Appendix 2. DATA DERIVATION DETAILS

Appendix 2.1. Definition and Use of Visit Windows in Reporting

Study visits are planned at Screening, Baseline and then at post-baseline Weeks 2, 4, 8, 12, 16, 24, and 40. If a subject discontinues from the trial then there will be an Early Termination Follow-Up period and for those who refuse, ideally, an Early termination visit. To account for this visit and any early or late scheduled visits (compared to the target study days) we define ‘windows’ to be able to allocate each efficacy observation to a single specific study visit. For the assessments made at each planned study visit (e.g. WOMAC subscales, Patient Global Assessment of Osteoarthritis etc.) these visit windows are shown below. When multiple observations occur in a visit window, the observation closest to the protocol specified target day will be used, noting that the latter will be used in the case of a tie.

Visit	Target Study Day	Window
Screening [1]	Variable (up to 37 days prior to baseline visit)	[No lower limit, Day -8]
Baseline	1 (defined as initial day of study drug administration)	[-7,1]
Week 2	15	[2,22]
Week 4	29	[23,43]
Week 8	57	[44,71]
Week 12	85	[72,99]
Week 16	113	[100,141]
Week 24	169	[142,197]

[1] Only efficacy data collected at screening is WOMAC Pain subscale

One additional window will be created relative to the date of last SC dose for summaries of efficacy data collected beyond the planned treatment period. This window will include data from 16 +/- 4 weeks past the date of the last SC dose. The target day is 113 days after the last SC dose, with a window of [85, 141] days after the last SC dose. If multiple observations occur in this visit window, the observation closest to the specified target day will be used, noting that the latter will be used in the case of a tie.

For the assessments not made at each planned study visit, broader visit windows are shown below. When multiple observations occur in a visit window, the observation closest to the protocol specified target day will be used, noting that the latter will be used in the case of a tie.

EQ-5D-5L

Visit	Target Study Day	Window
Baseline	1 (defined as initial day of study drug administration)	[-7, 1]
Week 8	57	[2, 85]
Week 16	113	[86, 141]

WPAI: OA

Visit	Target Study Day	Window
Baseline	1 (defined as initial day of study drug administration)	[-7,1]
Week 16	113	[2, 141]

HCRU

Visit	Target Study Day	Window
Baseline	1 (defined as initial day of study drug administration)	[no lower limit, 1]
Week 24	169	[2, 197]
Week 40	281	[198, no upper limit]

For the average pain in the index joint, the data are collected daily via electronic diary up to the end of Week 16, and thereafter Weekly up to Week 40. Data up to Week 16 will be reported as part of the efficacy assessment (summary up to Week 24; analysis up to Week 16).

The Baseline score is the mean of the last 3 non-missing pain scores over study days -7 to -1. If fewer than 3 are available between study days -7 and -1, the baseline will be the mean of the available scores.

The table below describes the visit days for each week (Weeks 1-16). All available on-treatment diary data in each of the weekly intervals will be used to calculate the mean daily pain score for that study week.

Study Week	Days	Study Week	Days
1	1-7	9	57-63
2	8-14	10	64-70
3	15-21	11	71-77
4	22-28	12	78-84
5	29-35	13	85-91
6	36-42	14	92-98
7	43-49	15	99-105
8	50-56	16	106-112

After the Week 16 visit, pain scores are captured only once a week in the diary. These are grouped in 4-week intervals using visit windows as shown below. If a subject comes in late for a Week 16 visit (or weekly diary is not activated at the visit), and so has daily diary data collected past Day 112, these data will be averaged with any data obtained weekly for any given interval. All available on- or off-treatment data will be used for these windows after the planned treatment period.

Summary Week	Includes Weeks	Days
20	17 - 20	113-140
24	21 - 24	141-168
28	25 - 28	169-196
32	29 - 32	197-224
36	33 - 36	225-252
40	37 - 40	253-280

One additional window will be created relative to the date of last SC dose for summaries of diary pain scores collected beyond the planned treatment period. This window will be identified as 16 Weeks Post Last Dose, and will include the average of all data from 13 to 16 weeks (85 to 112 days) past the date of the last SC dose. All available on- or off-treatment data will be used for this window after the planned treatment period.

Appendix 3. STATISTICAL METHODOLOGY DETAILS

Health State Utility of the EQ-5D-5L

The EQ-5D-5L contains five questions that measure the following dimensions: mobility, self-care, usual activities, pain/discomfort, and anxiety/depression. Each of the five dimensions has five levels: (1) no problems; (2), slight problems; (3) moderate problems; (4) severe problems; and (5) extreme problems.

The health utility scores are defined for every possible set of outcome combinations of the five dimensions for the following countries:

- Denmark, France, Germany, Japan, the Netherlands, Spain, Thailand, UK, US and Zimbabwe

It is intended that this study will recruit subjects from the following countries:

- US (including Puerto Rico), Canada.

Some of these may not actually recruit or treat subjects, and other countries may be added. As there is a mismatch between countries where subjects are being recruited and the currently available EQ-5D-5L health utility scoring, we will assign subjects to the following scoring countries based on the following assignments.

EQ-5D Scoring Country	Study Recruitment Country
Denmark	-
France	-
Germany	-
Japan	-
The Netherlands	-
Spain	-
Thailand	-
UK	-
US	US (including Puerto Rico), Canada
Zimbabwe	-

If more EQ-5D-5L utility scores become available or other countries are added, then this assignment may be modified.

The health utility for a patient with no problems in all 5 items is 1 for all countries (except for Zimbabwe where it is 0.9), and is reduced where a patient reports greater levels of problems across the five dimensions. The minimum score in US scoring is -0.109.

WPAI:OA Endpoints

The tables below summarize the 6 questions of the WPAI:OA questionnaire, and the four endpoints of the effect of impairment on activity and impairment.

Question	Question Wording	Scoring
1	Are you currently employed? [if No skip to question 6]	Yes, No
2	During the past seven days, how many hours did you miss from work due to problems associated with your OA of the knee or hip	number of hours (free text)
3	During the past seven days, how many hours did you miss from work because of any other reason, such as vacation, holidays, time off to participate in this study?	number of hours (free text)
4	During the past seven days, how many hours did you actually work (if '0' skip to Question 6)	number of hours (free text)
5	During the past seven days, how much did your OA of the knee or hip affect productivity while you were working?	0 to 10 scale with 0 being 'No effect on my work' and 10 being 'Completely prevented me from working'
6	During the past seven days, how much did your OA of the knee or hip affect your ability to do your regular daily activities, other than work at a job?	0 to 10 scale with 0 being 'No effect on my daily activities' and 10 being 'Completely prevented me from doing my daily activities'

WPAI endpoint	Calculation
Percent activity impairment due to Osteoarthritis	$Q6 * 10$
Percent impairment while working due to osteoarthritis	$Q5 * 10$
Percent overall work impairment due to osteoarthritis	$\left\{ \frac{Q2}{Q2 + Q4} + \left[1 - \left(\frac{Q2}{Q2 + Q4} \right) \right] \left(\frac{Q5}{10} \right) \right\} * 100$
Percent work time missed due to Osteoarthritis	$\frac{Q2}{Q2 + Q4} * 100$

Healthcare Resource Utilization (example using 3 month recall—8 week recall is also used in study)

Question	Response	Scoring

During the last 3 months, what services did you receive directly related to your osteoarthritis?
 
 • Primary Care Physician • Neurologist • Rheumatologist • Physician Assistant or Nurse Practitioner • Pain Specialist • Orthopedist • Physical Therapist • Chiropractor • Alternative Medicine or Therapy • Podiatrist • Nutritionist/Dietician • Radiologist • Home healthcare services • Other 	Number of Visits	Response not selected = 0 Number of visits = 1-999
During the past 3 months, have you visited the emergency room due to your osteoarthritis?	Yes, No	No = 0 Yes = 1
How many times?	Number of visits	0-999
During the past 3 months, have you been hospitalized due to your osteoarthritis?	Yes, No	No = 0 Yes = 1
How many nights in total did you stay in hospital due to your osteoarthritis in the last 3 months?	Number of Nights	0-999 (max should be 92)

Did you use these aids or devices to help you in doing things because of your osteoarthritis in the last 3 months?
 
 • Walking Aid • Wheelchair • Devices or utensils to help you dress, eat or bathe • Other 	Did not use any aids or devices Never, rarely, sometimes, often, always	Did not use any aids or devices = 0 Device not selected = 0 Never = 1 Rarely = 2 Sometimes = 3 Often = 4 Always = 5

Did you quit your job because of your osteoarthritis?	Yes, No	No = 0 Yes = 1 Not applicable = 2
How long ago did you quit your job because of your osteoarthritis?	Years and Months	0-99 Years and 0-99 Months (should be max of 11 months)

Rescue Medication Endpoints

Rescue medication data is collected daily using an electronic system up to Week 16, and weekly after Week 16 and up to Week 40. Daily and weekly collected data will be assigned to a specific study week for summary and reporting. The assignment of daily and weekly data to weeks will use the same principle as described above in Appendix 2.1 for the daily and weekly index joint pain data.

The incidence of rescue medication use will look for any incidence in the week of interest (collected through daily or weekly diary data). The number of days of RM use (using daily and weekly data) and the total amount taken (using daily data up to Week 16 only) over the week will be calculated for the assigned week algorithm described above.

Imputation is described in [Section 5.3](#) above. Imputation occurs for daily data up to Week 16 where the subject is in the trial and up to the end of that particular week.

An example of imputation and calculating the three endpoints using the daily diary data is shown below.

Example of calculating rescue medication data from Daily Diary Data (Subject does not discontinue)

In this example, a subject has a Week 2 visit on study day 14 (slightly earlier than the nominal day 15). Study days 8-14 would represent Week 2 data.

Using the Week 2 interval described above for a subject, i.e. study days [8-14], we have the following rescue medication example data.

The amount taken and number of days of rescue medication use is adjusted for the duration of the Weekly interval.

Study Day (Week)	Number of Doses of RM taken [1]	Number of Doses of RM taken [1] with LOCF imputation
8 (Week 2)	2	2
9 (Week 2)	Missing	2 [2]
10 (Week 2)	0	0
11 (Week 2)	1	1

12 (Week 2)	Missing	1 [2]
13 (Week 2)	2	2
14 (Week 2)	0	0

[1] 500mg tablets of acetaminophen; [2] Using LOCF imputation for missing data

For this subject the following data will be calculated for Week 2:

- Incidence of rescue medication taken in Week 2: Yes. Rescue medication taken on days 8, 9 (imputed), 11, 12 (imputed), 13.
- Number of days of rescue medication use in Week 2: 5. For days 8-14 we have rescue medication taken on days 8, 9 (imputed), 11, 12 (imputed), and 13. The number of days taken for the 7 day period is $5/7*7=5$.
- Amount (mg) of rescue medication use in Week 2: For days 8-14 we have the number of doses taken of 2, 2 (imputed), 0, 1, 1 (imputed), 2, and 0. The number of doses taken for the 7 day period is $8/7*7=8$, making the amount of acetaminophen dosage of 4000mg.

Example of calculating rescue medication data from Daily Diary Data (Subject discontinues)

In this example, a subject discontinues on study day 62, a few days after a Week 8 visit (which was on study day 60). The Week 5-8 data is calculated as described above (e.g. Week 8 using days [50, 56]). The subject has rescue medication data as shown below.

Study Day (Week)	Number of Doses of RM taken [1]	Number of Doses of RM taken [1] with LOCF imputation
57 (Week 9)	1	1
58 (Week 9)	1	1
59 (Week 9)	Missing	1 [2]
60 (Week 9)	Missing	1 [2]
61 (Week 9)	Missing	1 [2]
62 (Week 9)	Missing	1 [2]
63 (Week 9)	Missing	1 [2]

[1] 500mg tablets of acetaminophen; [2] Using LOCF imputation for missing data

Week 9 is calculated as days 57 to 63. The data up to the end of the last week the subject was in the trial is imputed using LOCF as shown above. Therefore the Week 9 scores are then used to impute the Weekly data for summary and analysis for Weeks 10 to 16.

As above the incidence of rescue medication for Week 9 would be ‘Yes’. The number of days of rescue medication use would be 7, and the average dose would be $7/7*7*500=3500\text{mg}$ for this week.

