The rescue medication data will be converted to Weekly scores for the week prior to the timepoint of interest. Calculation of the endpoints is described in Appendix 3.

The ... number of days of use of rescue medication ... will be analyzed for Weeks 2, 4, 8, 12, and 16... and the amount of rescue medication use per week will be analyzed for Weeks 2, 4, 8, 12, and 16. ... The number of days and amount of rescue medication (mg dosage of acetaminophen) will be analyzed using the Negative Binomial model, with model terms of Baseline WOMAC Pain subscale score, Baseline diary average pain score, index joint, Kellgren-Lawrence grade, and treatment group. In this model the error term is defined with a negative binomial distribution, and 'log' is used as the link function. Estimated levels of rescue medication use will be shown for each treatment group, and the ratio (with 95% CI) for comparisons versus placebo will be shown. Imputation for missing rescue medication data will use LOCF only. For this analysis, Baseline data will not be carried forward in the case of a post-Baseline observation not being available for use in LOCF.

A table showing number and percentage of subjects will summarize the response for each dimension (item) for the EQ-5D-5L™ at Baseline and Week 8 and Week 16. These summary tables will be shown by treatment group. In addition, for each treatment and for each time point assessed, descriptive statistics (mean, standard deviations, median, number of subjects) will characterize the five-item health status profile on the EQ-5D-5L™ in terms of the health utility score, and the EQ-Visual Analog Scale (EQ-VAS).

The HCRU data at Baseline, Week 24, and Week 40 will be summarized.

Summaries of the change from Baseline to Week 16 in the WPAI:OA impairment scores will be shown by treatment group. This summary will use observed data only (no imputation for missing data). The calculation of these endpoints is described in Appendix 3.

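### Appendix 3 gives no rule for scoring overall work impairment when no hours were worked; coded as printed, the formula turns a determinable score of 100% into a missing value

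*SAP*

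**What the plan says.** The WPAI:OA tables in SAP Appendix 3 list six questions and four derived scores. Two skip rules matter here.

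- Q1: "Are you currently employed? [if No skip to question 6". Subjects who are not employed answer only Q6, so the point concerns employed subjects alone.
- Q4: "During the past seven days, how many hours did you actually work", with an instruction to go to Q6 if the answer is 0. An employed subject who worked no hours is never asked Q5, the rating of productivity while working.

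Q2 asks "how many hours did you miss from work due to problems associated with your OA of the knee or hip". Two of the scores divide by the sum of Q2 and Q4:

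- "Percent work time missed due to Osteoarthritis" = Q2/(Q2+Q4) × 100. It does not use Q5.
- "Percent overall work impairment due to osteoarthritis" = {Q2/(Q2+Q4) + [1 − Q2/(Q2+Q4)] × (Q5/10)} × 100. It does use Q5, and no separate rule is given for Q4 = 0.

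On missing data, Section 5.2.2 says of WPAI: "This summary will use observed data only (no imputation for missing data). The calculation of these endpoints is described in Appendix 3". Appendix 1 likewise lists the WPAI ANCOVA as observed data. Section 5.2.2 analyses all four scores with the ANCOVA used for the primary endpoint, with the corresponding Baseline score as a covariate.

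**The concern.** Three provisions that are each reasonable do not fit together. The form skips Q5 when no hours were worked, the formula contains Q5, and missing values are not imputed. The subjects caught between them are employed people who missed all their work time because of osteoarthritis, and theirs is the highest score the scale allows.

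The ANCOVA models change to Week 16 with Baseline as a covariate, so a missing score at either visit removes the subject. A subject fully absent at Week 16 is one of the worst outcomes. A subject fully absent at Baseline who later returned to work could be among the largest improvers. Full absence at Week 16 arises after randomization and treatment may influence it, so losing those scores can affect the comparison of arms as well as the group means. The table of decreases, no changes and increases would lose the same subjects. They would still appear at 100% in percent work time missed, and nothing in the SAP would alert a reader to the difference.

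**Working it through.** The SAP gives no worked WPAI example and no expected WPAI values, so there is no stated figure to reproduce. The check evaluates the two Appendix 3 formulas as printed. Write r = Q2/(Q2+Q4).

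**1. Ordinary case (Q2 = 8, Q4 = 32, Q5 = 5).** r = 8/40 = 0.20. Work time missed = 20%. Overall work impairment = {0.20 + 0.80 × 0.5} × 100 = 60%. The formulas behave as intended.

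**2. Whole week lost to osteoarthritis (Q2 = 40, Q4 = 0, Q5 skipped).** r = 40/40 = 1. Work time missed = 100%. Overall work impairment = {1 + (1 − 1) × missing} × 100. Coded literally, zero times missing is missing, so the score is missing.

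**3. The same case with Q5 supplied.** For each Q5 from 0 to 10, overall work impairment = {1 + 0 × (Q5/10)} × 100 = 100%. Q5 cannot change the result, and Q2 and Q4 alone determine it.

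**4. One hour worked (Q2 = 39, Q4 = 1).** r = 0.975. Overall work impairment = 97.5% if Q5 = 0 and {0.975 + 0.025 × 1} × 100 = 100% if Q5 = 10. A subject who worked one hour is kept with a score between 97.5% and 100%, while a subject who worked none is lost.

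**5. No hours worked, none missed for osteoarthritis (Q2 = Q4 = 0).** r = 0/0. Both work time missed and overall work impairment are undefined, and the SAP has no rule for either.

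**6. Size, on assumed inputs.** Let s be the share of employed subjects in case 2 and m the mean score of the others. The mean with them included is 100s + (1 − s)m. With them dropped it is m. The understatement is s × (100 − m):

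| s (assumed) | m = 20 | m = 40 | m = 60 |
|---|---|---|---|
| 1% | 0.8 | 0.6 | 0.4 |
| 2% | 1.6 | 1.2 | 0.8 |
| 5% | 4.0 | 3.0 | 2.0 |

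These are shifts, in points, of a raw group mean. The planned contrast is adjusted for Baseline, where the relevant quantity is 100 minus the value predicted from Baseline. If fully absent subjects tend to have high Baseline scores, that is smaller than 100 − m.

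**7. Numbers of subjects.** Section 2.2 plans about 230 per arm. If 40% to 60% are employed (assumed), that is 0.40 × 230 = 92 to 0.60 × 230 = 138 employed per arm, so 1% is about one subject.

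**The case against.** The strongest reply is that no passage sets these scores to missing or excludes these subjects. The printed formula gives 100% for any Q5, so a careful programmer would assign 100. Appendix 3 introduces its tables as summaries, and handling of a skipped item commonly sits in dataset specifications that are not shown here. The four WPAI scores have different denominators by design, so a difference in subjects between two of them is not a fault in itself. Subjects lost because of a Baseline value are balanced between arms in expectation. Few subjects are likely to be affected, and Section 5.1.2 limits type I error control to the co-primary endpoints and the key secondary endpoint, which excludes WPAI.

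Most of this stands as a limit on the point. The loss depends on literal coding, the raw-mean shifts overstate what may reach the adjusted contrast, and no decision rule depends on WPAI. Losing fully absent subjects at Baseline would change the population analysed without favouring an arm in expectation.

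It does not remove the gap. Sections 3.2.1 and 5.2.2 both name Appendix 3 as the place where the calculation is described. Two programmers could follow it faithfully and obtain different analysis populations. The SAP settles comparable cases elsewhere: Section 5.3 says what happens when components of the OMERACT-OARSI index are missing at Baseline, and Appendix 3 works through missing days in the rescue medication diary. For WPAI the skip rule guarantees a missing component, and no rule follows.

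**Conclusion.** The point holds as a gap in the scoring rule. Taken together, the printed formula, the skip at Q4 and the observed-data rule lose scores that Q2 and Q4 already fix at 100%, if the formula is coded as it stands. The loss is selective, because it falls only on the maximum score.

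A reader might go further and infer that the SAP drops these subjects, or that the treatment contrast is biased by a known amount. The document supports neither. It nowhere says they are excluded, and it gives no employment rate, absence rate or WPAI mean from which a bias could be computed. The figure of about 0.4 to 0.8 points per 1% of employed subjects affected rests on an assumed mean of 60 to 20 for the others and applies to a raw group mean.

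The consequence is confined to one secondary endpoint outside the multiplicity-controlled tests. The correction is still worth making, because it follows from the SAP's own algebra and costs almost nothing.

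**What to change.** Add to the WPAI:OA part of Appendix 3, to apply at Baseline and at Week 16:

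- If Q1 = Yes, Q2 > 0 and Q4 = 0, set percent overall work impairment to 100.
- If Q1 = Yes, Q2 = 0 and Q4 = 0, set both percent overall work impairment and percent work time missed to missing, since the ratio is 0/0.

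Percent impairment while working needs no change: it is not applicable when no hours were worked.

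The cost is two lines in the derivation. No new data are needed and the model is unchanged. The rule is consistent with using observed data only, because the value of 100 is calculated from answers that were collected. It should be fixed before unblinding.

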Appendix 3.1. Further Details of Interim Analyses

Details of the ongoing review of safety data (including joint safety events) are given in a separate statistical analysis plan for the Data Monitoring Committee.

Appendix 3.2. Further Details of the Statistical Methods

A description of the combination of the ANCOVA results from each of the multiple imputed datasets is given below, and taken from Little & Rubin (2002), page 86-7.

In this analysis we have defined the number of imputations (D) to be 100.

The treatment estimates for individual treatment groups and treatment contrasts are defined as θ_i for $i = 1K D$. The combined estimate is $\bar{\theta}_D = \frac{1}{D} \sum_{i=1}^D \theta_i$. The variability of the combined estimate contains components of both Within- (W) and Between- (B) imputation dataset variability. These are shown below:

$$\bar{W}_D = \frac{1}{D} \sum_{i=1}^D W_i \text{ and } B_D = \frac{1}{D-1} \sum_{i=1}^D (\hat{\theta}_i - \bar{\theta}_D)^2$$

where W_i is the variance for the parameter θ_i .

The total variance for $\bar{\theta}_D$ is shown below:

$$T_D = \bar{W}_D + \frac{D+1}{D} B_D.$$

The test statistic $\frac{(\theta - \bar{\theta}_D)}{\sqrt{T_D}}$ has a t-distribution with v^* degrees of freedom, which is defined below:

$$v^* = \left(\frac{1}{v} + \frac{1}{\hat{v}_{obs}} \right),$$

using

$$v = (D-1) \left(1 + \frac{1}{D+1} \frac{\bar{W}_D}{B_D} \right)^2$$

$$\hat{v}_{obs} = (1 - \hat{\gamma}_D) \left(\frac{v_{com} + 1}{v_{com+3}} \right) v_{com}$$

$$\hat{\gamma}_D = \left(1 + \frac{1}{D} \right) \frac{B_D}{T_D}.$$

This distribution can be used to construct the test statistics and 95% confidence intervals for θ .

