2.2. Study Design

The study design is summarized in the diagram below.

Figure 1. Study Design

This is a randomized, double-blind, placebo-controlled, multicenter, parallel-group, Phase 3 study of the efficacy and safety of tanezumab when administered by SC injection for 16 weeks compared to placebo in subjects with osteoarthritis of the knee or hip. Approximately 690 subjects (approximately 230 per treatment group) will be randomized to one of 3 treatment groups in a 1:1:1 ratio. Subjects will receive a total of two SC injections, separated by 8 weeks:

- *tanezumab 2.5 mg (Day 1) and tanezumab 2.5 mg (Week 8);*
- *tanezumab 2.5 mg (Day 1), and tanezumab 5 mg (Week 8);*
- *placebo to match tanezumab (Day 1) and placebo to match tanezumab (Week 8).*

The randomization will be stratified by the factors of index joint and highest Kellgren-Lawrence grade in the knee and hip joints.

This study is designed with a total (post-randomization) duration of 40 weeks and will consist of three periods: Screening (up to a maximum of 37 days), Double-blind Treatment (16 weeks, 6 in-clinic visits), and Safety Follow-up (24 weeks). The Screening Period (to begin up to 37 days prior to Randomization) includes a Washout Period (lasting a minimum of 2 days for all prohibited pain medications) if required, and an Initial Pain Assessment Period (IPAP; 7 days prior to Randomization/Baseline; minimum 3 days).

The end of treatment period is at Week 16, with the safety follow-up period up to Week 40. The primary time point for efficacy is Week 16. The period of interest for most safety results is the treatment period. Selected safety results will also be provided separately for the safety follow-up period, and some results will be provided for the combined overall study period comprising the treatment and safety follow-up periods.

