5. GENERAL METHODOLOGY AND CONVENTIONS

5.1. Hypotheses and Decision Rules

5.1.1. Statistical Hypotheses

The treatment comparisons being made in this study are tanezumab 2.5 mg and 2.5 mg then 5 mg (2.5/5 mg) versus placebo. For these treatment comparisons, the null and alternative hypotheses are shown below (note $\mu_{\text{TREATMENT}}$ relates to the mean change from Baseline for the specified treatment group). All tests will be 2-sided.

Null Hypotheses	H0: $\mu_{\text{TANEZUMAB 2.5mg}} - \mu_{\text{PLACEBO}} = 0$
	H0: $\mu_{\text{TANEZUMAB 2.5/5mg}} - \mu_{\text{PLACEBO}} = 0$
Alternative Hypotheses	H1: $\mu_{\text{TANEZUMAB 2.5mg}} - \mu_{\text{PLACEBO}} \neq 0$
	H1: $\mu_{\text{TANEZUMAB 2.5/5mg}} - \mu_{\text{PLACEBO}} \neq 0$

The hypotheses for other types of analyses (e.g. for the binary response endpoints) would be similar to those shown above.

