5.1.2. Statistical Decision Rules

The Type I error rate (α -level) used in the assessment of pair-wise treatment comparisons for the primary efficacy endpoints is 5%. The fixed sequence testing strategy of the co-primary endpoints is described below.

The assessment of significance for the tanezumab versus placebo treatment contrasts will use a step-down testing strategy within each of the co-primary efficacy endpoints. The step-down testing will first test tanezumab 2.5/5 mg versus placebo, and if statistically significant ($p \leq 0.05$) will then test tanezumab 2.5 mg versus placebo. Finally, the particular tanezumab dose group is declared as superior to placebo if the corresponding treatment contrast is significant over all three co-primary endpoints. This testing procedure will maintain the Type I error to 5% or less within each of the co-primary efficacy endpoints, and to less than 5% for all three co-primary efficacy endpoints.

The secondary endpoint of subjects with $\geq 50\%$ reduction from baseline in WOMAC Pain at Week 16 is identified as a key secondary endpoint and will be included in the testing strategy. If both tanezumab regimens are found to be statistically significantly better than placebo in the primary comparisons described above, the two comparisons of this secondary endpoint (tanezumab 2.5 mg treatment group versus placebo and tanezumab 2.5/5 mg treatment group versus placebo) will be adjusted for multiple comparisons using the Hochberg procedure and an overall significance level of 0.05.

The primary analysis will be that with the multiple imputation approach (see below for details), and thus the overall type I error is controlled for each of the two dose regimens (2.5 mg and 2.5/5 mg) since all three co-primary endpoints need to be significant for a single dose. The overall type I error of the study is also controlled given the step-down testing strategy for each of the primary endpoints and the key secondary endpoint. Control of the type I error rate accounting for multiplicity of contrasts will only apply to the three co-primary endpoints (model with the primary imputation analysis) and the key secondary endpoint.

Regardless of the outcome of the primary and key secondary analyses, the secondary endpoints will be tested. No adjustment for multiple comparisons will be made for the secondary efficacy, and for the safety endpoints. The α -level for each hypothesis test for the secondary and exploratory analyses will be 5%.

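### SAP Appendix 3.2 prints the multiple-imputation degrees of freedom with 1/(D+1) where D/(D+1) is needed, which makes the pooled co-primary tests slightly too conservative

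*SAP*

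**What the plan says.** SAP Sections 5.2.2 and 5.3 make a multiply imputed ANCOVA the primary analysis of WOMAC Pain, WOMAC Physical Function and the Patient's Global Assessment at Week 16. Section 5.3 sends the reader to Appendix 3.2 for how the imputed results are combined.

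That appendix states: "In this analysis we have defined the number of imputations (D) to be 100". With W the mean within-imputation variance and B the between-imputation variance, it defines:

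- total variance: T = W + ((D+1)/D)·B
- missing-information fraction: γ = (1 + 1/D)·B/T
- degrees of freedom: "v = (D-1) \left(1 + \frac{1}{D+1} \frac{\bar{W}_D}{B_D} \right)^2"
- v_obs, built from γ and the complete-data degrees of freedom v_com
- v*, which combines v and v_obs and is the df of the t-distribution used for tests and intervals

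The results feed a hard gate. Under Section 5.1.1, "All tests will be 2-sided". Under Section 5.1.2, 2.5/5 mg is tested first within each endpoint and, "if statistically significant ($p \leq 0.05$) will then test tanezumab 2.5 mg versus placebo". A regimen is declared superior only if it is significant on all three endpoints.

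**The concern.** The bracket in v should be the reciprocal of the missing-information fraction, so that v = (D−1)/γ². The printed bracket is not that reciprocal: W/B is multiplied by 1/(D+1) instead of D/(D+1). When little information is missing, v should become very large, because the pooled test is then almost a complete-data test. The printed v instead stays close to its floor of D−1 = 99 unless imputation adds almost no variance.

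At stake is the prespecified reference distribution of the confirmatory tests. If the formula is programmed as printed, co-primary p-values and intervals are slightly wrong. If software with the usual pooling rule is used, the reported analysis departs from the SAP's own formula. Nothing elsewhere in the SAP corrects it.

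**Working it through.** **Inputs from the SAP.** D = 100 and the formulas for T, γ and v_obs (Appendix 3.2); two-sided 5% tests (Sections 5.1.1 and 5.1.2); about 690 randomized subjects (Section 2.2), used only to choose a plausible v_com.

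**Assumptions, because the SAP gives no values.** v_com = 680, repeated at 600. Relative variance increase r = (1 + 1/D)·B/W from 0.02 to 0.5. v_obs is read as (1−γ)·((v_com+1)/(v_com+3))·v_com, and v* as 1/(1/v + 1/v_obs).

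**Step 1: the coefficient.** From the SAP's T and γ:

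1/γ = T / [((D+1)/D)·B] = 1 + [D/(D+1)]·(W/B)

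Treating W as fixed and B as having D−1 degrees of freedom, a Satterthwaite match on T gives

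v = (D−1)/γ² = (D−1)·(1 + [D/(D+1)]·W/B)²

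At D = 100 the coefficient should be 100/101 = 0.990. The printed one is 1/101 = 0.0099.

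**Step 2: v in terms of r.** Since W/B = 1.01/r:

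- correct: v = 99·(1 + 1/r)²
- printed: v = 99·(1 + 0.01/r)²

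At r = 0.02 these are 99 × 51² = 257,499 and 99 × 1.5² = 222.8. At r = 0.1 they are 99 × 11² = 11,979 and 99 × 1.1² = 119.8. The correct values equal 99/γ² at every r tried.

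**Step 3: effect on the test (v_com = 680).**

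| r | v correct | v printed | v* correct | v* printed | t correct | t printed | excess CI width | correct p = 0.050 reads as |
|---|---|---|---|---|---|---|---|---|
| 0.02 | 257,499 | 223 | 663 | 167 | 1.964 | 1.974 | 0.55% | 0.0512 |
| 0.05 | 43,659 | 143 | 636 | 117 | 1.964 | 1.981 | 0.85% | 0.0519 |
| 0.1 | 11,979 | 120 | 586 | 100 | 1.964 | 1.984 | 1.01% | 0.0523 |
| 0.2 | 3,564 | 109 | 488 | 91 | 1.965 | 1.986 | 1.09% | 0.0525 |
| 0.3 | 1,859 | 106 | 407 | 88 | 1.966 | 1.987 | 1.09% | 0.0525 |
| 0.5 | 891 | 103 | 300 | 84 | 1.968 | 1.989 | 1.05% | 0.0524 |

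The smallest correct p that the printed rule would turn into 0.050 is 0.0476. With v_com = 600, v* is 585 to 275 correct against 161 to 82 printed, and the excess width is again 0.5% to 1.1%.

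**Step 4: simulation.** With W known, 500,000 draws at each γ from 0.05 to 0.50 gave rejection rates under the null of 0.0496 to 0.0505 with the corrected v and 0.0472 to 0.0483 with the printed v. The corrected formula holds the nominal 5%; the printed one falls slightly below it. For γ from 0.01 to 0.50, the calculated loss of power is at most about 0.6 percentage points at 80% power and 0.4 at 90%.

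**The case against.** The strongest objection is that the whole point turns on one character in an equation read from a PDF, and the same block shows other signs of imperfect reading. The index range is garbled, the +3 in v_obs sits inside a subscript, and v* appears as a bare sum with no power of −1. Taken literally, that v* would be about 0.006 to 0.012 over the range above, which is no usable test. The mild consequence described here therefore depends on repairing v* and v_obs first. That dependence is real and is listed among the assumptions; the missing power of −1 is not counted as an error. A misreading of v itself is less likely. Its fraction is complete and well formed, and the other fractions in D on the same page were read correctly.

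A second objection is that the SAP never writes v = (D−1)/γ², so this is not one sentence contradicting another. That is true, but the relation follows from the SAP's own T by a standard argument, and the simulation supports it.

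Third, Section 5.3 says that standard combination methods will be used, so routine software may bypass the printed formula altogether. This lowers the practical risk, but Section 5.3 names Appendix 3.2 as the description of those methods, so the stated rule remains wrong.

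**Conclusion.** The concern holds and is minor. As the appendix reads, v has 1/(D+1) where D/(D+1) is required, and the W/B term is 100 times too small at D = 100. Because v cannot fall below 99, the damage is limited: intervals 0.5% to 1.1% too wide, and a step-down decision at risk only for a correct p between about 0.0476 and 0.050. Estimates, T and standard errors are right, and type I error is not inflated. These sizes rest on the assumed v_com and r and on reading v* as the inverse of the printed sum. The error in the coefficient itself depends on neither v_com nor r.

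**What to change.** In Appendix 3.2, replace 1/(D+1) by D/(D+1), so that v = (D−1)·(1 + [D/(D+1)]·W/B)², or write the equivalent (D−1)/γ². At the same time check v, v_obs and v* against the source page. Confirm that the denominator in v_obs is v_com + 3 and that v* is (1/v + 1/v_obs)⁻¹, and restore either one if it is really misprinted. The cost is SAP wording only; design, data collection and trial conduct are untouched.
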